5.4.3 Exploratory Assessments

The exploratory assessments collected in the maintenance phase will be summarised for the full analysis set and the exploratory assessments collected in the open-label phase will be summarised for the open-label full analysis set. For all exploratory assessments the observations at visit 2 will be used for the purpose of summarising the change from visit 1 in the open-label phase.

5.4.3.1 Proportion of subjects still at risk of first relapse at week 26 and week 52

In section 11.3.3.3 of the protocol on the analysis of the primary endpoint, it is described that the proportion of subjects still at risk for a first relapse will be compared between the two treatment groups at 26 weeks and 52 weeks after randomisation. This will be considered as two explorative endpoints on its own. The comparison will be done by using an unpaired z-test. In addition, a binomial test will be done. The proportions and the corresponding standard errors will be obtained from the estimated survival curves for the primary endpoint. The estimates of proportions, the 95% confidence intervals and p-value will be presented.

More details for the tables and listings can be found in [Appendix I](#) and [Appendix II](#).

5.4.3.2 m-PASI

Open-label phase:

m-PASI will be summarised by visit. Change and percent change in m-PASI from visit 1 to visit 2 will also be summarised.

Maintenance phase:

m-PASI when the subject is not initiating, ending or in a relapse period will be summarised by visit and by treatment group.

m-PASI collected when the subject is initiating a relapse period will be summarised by visit and visit intervals and by treatment group.

m-PASI collected when the subject is ending a relapse period will be summarised by visit and visit intervals and by treatment.

Trial ID: LP0053-1004	Date: 15-JUL-2019	Version: 1.0 Page 18 of 177
-----------------------	-------------------	--------------------------------

Change and percent change in m-PASI from start of relapse to end of relapse will be summarised by visit for start of relapse and by treatment group.

m-PASI collected at visits where the subject is in a relapse period, will be listed only.

See section [5.7](#) for details regarding changes as compared to the protocol.

More details for the tables and listings can be found in [Appendix I](#) and [Appendix II](#).

5.4.3.3 Physician's Global Assessment of Disease Severity

Open-label phase:

Physician's global assessment of disease severity (PGA) will be summarised by visit. A shift table for categories of PGA at visit 1 versus the category at visit 2 will also be done.

Maintenance phase:

PGA collected when the subject is not initiating, ending or in a relapse period will be summarised by visit and by treatment group.

PGA collected when the subject is initiating a relapse period will be summarised by visit and visit intervals and by treatment group.

PGA collected when the subject is ending a relapse period will be summarised by visit and visit intervals and by treatment group.

A shift table for categories of PGA at start of relapse versus the category at end of relapse will also be done by visit for start of relapse and by treatment group.

PGA collected at visits in the maintenance phase, when the subject is in a relapse period will be listed only.

See section [5.7](#) for details regarding changes as compared to the protocol.

More details for the tables and listings can be found in [Appendix I](#) and [Appendix II](#).

5.4.3.4 Subjects in remission at each visit

The number of subjects in remission will be summarised as described in the protocol section 11.3.4.2 for scheduled visits.

A stack plot over subjects in remission by scheduled visits will be presented.

Trial ID: LP0053-1004	Date: 15-JUL-2019	Version: 1.0 Page 19 of 177
-----------------------	-------------------	--------------------------------

Further details for the table can be found in [Appendix I](#) and [Appendix II](#).

5.4.3.5 Time to when PASI75 is no longer fulfilled

The endpoint will not be analysed. See section [5.7](#) regarding details of changes as compared to the protocol.

5.4.3.6 Time to first relapse according to m-PASI

The endpoint will not be analysed. See section [5.7](#) regarding details of changes as compared to the protocol.

5.4.3.7 Efficacy after treatment of relapse

Efficacy after treatment of relapse is defined as the proportion of subjects with ‘clear’ or ‘almost clear’ according to the PGA after treatment of relapse. The endpoint will be summarised as described in section 11.3.4.5 of the protocol.

A stack plot over proportion of subjects with ‘clear’ or ‘almost clear’ according to the PGA after treatment of relapse by treatment group and relapse number will be presented.

More details for the table can be found in [Appendix I](#) and [Appendix II](#).

5.4.3.8 Target lesion/location scores

Open-label phase:

Target lesion/location will be summarised by visit. A shift table for categories of target lesion/location scores at visit 1 versus the category at visit 2 will also be done.

Maintenance phase:

Target lesion/location scores collected when the subject is not initiating, ending or in a relapse period will be summarised by visit and by treatment group.

Target lesion/location scores collected when the subject is initiating a relapse period will be summarised by visit and visit intervals and by treatment group.

Target lesion/location scores collected when the subject is ending a relapse period will be summarised by visit and visit intervals and by treatment group.

Trial ID: LP0053-1004	Date: 15-JUL-2019	Version: 1.0 Page 20 of 177
-----------------------	-------------------	--------------------------------

A shift table for categories of target lesion/location scores at start of relapse versus the category at end of relapse will also be done by visit for start of relapse and by treatment group.

Target lesion/location scores collected when the subject is in a relapse period will be listed only.

See section [5.7](#) for details regarding changes as compared to the protocol.

More details for the tables and listings can be found in [Appendix I](#) and [Appendix II](#).

5.4.3.9 Body Surface Area

Body surface area (BSA) should be interpreted as the percentage of BSA affected by psoriasis.

Open-label phase:

The percentage of BSA affected by psoriasis will be summarised by visit. Change and percent change in the affected BSA from visit 1 to visit 2 will also be summarised.

Maintenance phase:

The percentage of BSA affected by psoriasis collected when the subject is not initiating, ending or in a relapse period will be summarised by visit and by treatment group.

The percentage of BSA affected by psoriasis collected when the subject is initiating a relapse period will be summarised by visit and visit intervals and by treatment group.

The percentage of BSA affected by psoriasis collected when the subject is ending a relapse period, will be summarised by visit and visit intervals and by treatment group.

Change and percent change in the affected BSA from start of relapse to end of relapse will be summarised by visit for start of relapse and by treatment group.

The percentage of BSA affected by psoriasis collected when the subject is in a relapse period, will be listed only.

See section [5.7](#) for details regarding changes as compared to the protocol.

More details for the tables and listings can be found in [Appendix I](#) and [Appendix II](#).

Trial ID: LP0053-1004	Date: 15-JUL-2019	Version: 1.0 Page 21 of 177
-----------------------	-------------------	--------------------------------

5.4.3.10 Number of active treatment days during maintenance phase

The number of active treatment days during maintenance phase will be normalised by time of exposure and summarised by treatment group.

For the active treatment group, the number of active treatment days is calculated as the sum of days where treated with maintenance treatment (twice weekly) and days where treated with rescue IMP. A day in relapse where treated with both maintenance medication and rescue IMP will count as one active treatment day.

For the vehicle group, the number of active treatment days during the maintenance phase is calculated as the sum of days where treated with rescue IMP.

The number of active treatment days during maintenance phase will also be listed.

More details for the tables and listings can be found in [Appendix I](#) and [Appendix II](#).

5.4.4 Patient-Reported Outcomes

Patient reported outcomes collected in the maintenance phase will be analysed for the full analysis set. Patient reported outcomes collected in the open-label phase will be analysed for the open-label full analysis set.

5.4.4.1 Dermatology Life Quality Index (DLQI)

Open-label phase:

Dermatology life quality index (DLQI) will be summarised by visit. Change and percent change in DLQI from visit 1 to visit 2 will also be summarised.

Maintenance phase:

DLQI collected when the subject is not initiating, ending or in a relapse period will be summarised by visit and by treatment group.

DLQI collected when the subject is initiating a relapse period will be summarised by visit and visit intervals and by treatment group.

DLQI collected when the subject is ending a relapse period will be summarised by visit and visit intervals and by treatment group.

Trial ID: LP0053-1004	Date: 15-JUL-2019	Version: 1.0 Page 22 of 177
-----------------------	-------------------	--------------------------------

Change and percent change in DLQI from start of relapse to end of relapse will be summarised by visit for start of relapse and by treatment group.

DLQI collected when the subject is in a relapse period will be listed only.

See section [5.7](#) for details regarding changes as compared to the protocol.

Details on total DLQI scores calculation:

The total DLQI score will be presented in all above mentioned tables. The total DLQI score is calculated by summing the score of each question. If one question is left unanswered, this is scored 0, and the total score is calculated as usual. If two or more questions are left unanswered, no total score is calculated. The questions 1-6 and 8-10 are scored as described in [Table 4](#). Question 7 is scored as described in [Table 5](#). The total DLQI score ranges from 0 (no quality of life impairment) to 30 (maximal quality of life impairment).

Table 4: Scoring of DLQI question 1-6 and 8-10

Answer	Score
Very much	3
A lot	2
A little	1
Not at all	0
Not relevant	0
Unanswered	0

Table 5: Scoring of DLQI question 7

Answer		
Main part of question 7	Subpart of question 7	
Yes	Unanswered	3
Not relevant	Unanswered	0
No	A lot	2
No	A little	1
No	Not at all	0
No	Unanswered	0

If the main part of question 7 is answered with ‘Yes’, and the subpart is not left unanswered, the score will remain 3. If the main part of question 7 is answered with ‘Not relevant’, and the

Trial ID: LP0053-1004	Date: 15-JUL-2019	Version: 1.0 Page 23 of 177
-----------------------	-------------------	--------------------------------

subpart of the question is answered with ‘A lot’ or ‘A little’, the score will be 2 or 1 respectively.

Multiple imputation:

Missing DLQI total scores will be imputed using multiple imputation with 100 copies (seed=70309491) described in the steps below.

Missing assessment of the DLQI total score in-between non-missing assessments in the maintenance phase will not be imputed. The imputation step will depend on whether the reason for withdrawal for the subject to be imputed could potentially be related to IMP or not.

Imputation for subjects withdrawn with reasons ‘withdrawal by subject’ or ‘lost to follow up’:
This approach assumes that in the unobserved part of maintenance phase, the subject will behave similar to the observed part of the maintenance phase for subjects in the same treatment group completing the maintenance phase.

Imputation steps:

1. DLQI data and relapse status from one subject in the sub-set of subjects that completed their maintenance phase and are in the same treatment group as the withdrawn subject will be randomly selected. This will be referred as ‘sampled data’ in step 2.
2. Missing visits for the withdrawn subject will be inputted using the relevant visits from the sampled data.
3. Steps 1 and 2 will be repeated 100 times for each withdrawn subject to form 100 complete datasets

Imputation subjects withdrawn with reasons ‘adverse event’, ‘death’, ‘lack of efficacy’, or ‘subject not achieving clear or almost clear after treatment of relapse’:

This approach assumes that the subjects behave similarly in the unobserved part of the trial as the observed part for subjects leaving the trial for the same reasons independent of treatment group.

Imputation steps:

1. Total DLQI scores and corresponding relapse status from subjects withdrawn from the trial due to ‘adverse event’, ‘death’, ‘lack of efficacy’, or ‘subject not achieving clear or almost clear after treatment of relapse’ will be collected as one set of data.

Trial ID: LP0053-1004	Date: 15-JUL-2019	Version: 1.0 Page 24 of 177
-----------------------	-------------------	--------------------------------

2. A total DLQI scores will be sampled for each scheduled visit from the above collection of data (step 1).
3. Steps 1 and 2 will be repeated 100 times for each withdrawn subject to form 100 complete datasets

Imputation for subjects leaving the trial due to other reasons:

For cases with withdrawal reason specified as 'Other', the details will be revised on a blinded manner, selecting and documenting the imputation approach in the Analysis Set Definition Document.

Statistical analysis:

For each of the 100 complete datasets the total DLQI scores will be analysed using a Mixed effect Model Repeated Measurement (MMRM) with treatment group, visit (scheduled), interaction between treatment and visit, relapse status, and maintenance baseline total DLQI score as fixed factors and subject as random effect. Repeated measurements within subject is modelled using an unstructured variance structure. REML will be used for estimation.

The estimates and standard errors from the 100 analyses will be pooled into estimated least squares means for each treatment group and estimated treatment difference with associated standard errors using Rubin's rule to draw inference. From these pooled treatment estimates, the 95% CI for the treatment difference will be calculated. The p-value for treatment difference will be calculated using a two-tailed Student's t-test based on the pooled estimate. Pooled treatment estimates together with treatment difference, 95% CI and p-value will be presented by visit. Furthermore, the pooled treatment estimates will be plotted by visit.

See section [5.7](#) for details regarding changes as compared to the protocol.

More details for the tables and listings can be found in [Appendix I](#) and [Appendix II](#).

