6.3 Randomisation

Subjects will be randomised in a 1:1 ratio to receive LEO 90100 or vehicle twice weekly during the maintenance phase. Randomisation will be stratified by trial site, HPA axis testing, and by baseline disease severity (mild, moderate, severe).

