11.3.8 General Principles

All significance tests will be two-sided using the 5% significance level. All confidence intervals will be presented with 95% degree of confidence.

An observed cases approach will be used for tabulations of data by visit (i.e. involving only those subjects who attended each specific visit).

Categorical data will be summarised using the number and percentage of subjects in each category and treatment group. Continuous data will be summarised using the mean, median, standard deviation (SD), minimum and maximum values.

All the analyses specified in the protocol will be reviewed in relation to the blinded data actually obtained and the statistical analysis plan update will be finalised before breaking the randomisation code.

The randomisation is stratified by treatment group, trial site, HPA axis testing and disease severity at baseline as factors. Usually, the statistical analysis of efficacy parameters takes all the stratification factors into account. However, the HPA axis test is a safety parameter, which is only determined at a small subset of sites and subjects. Hence stratification by HPA axis test is not applicable for all sites. Also, it is expected that two subjects per site will be randomised. This means that a statistical model having HPA axis testing as a factor may not converge, depending on whether subjects participating in the HPA axis test drop out. Furthermore, the inclusion criteria for participating in the HPA axis test are “Moderate” or “Severe” in the baseline PGA assessment and a baseline BSA between 10 and 30%. Including the stratification factor HPA axis testing would therefore introduce a confounding with the

stratification according to baseline PGA as well as sites. Therefore the stratification according to HPA axis testing is not included in the statistical analyses.

Any changes from the statistical analysis planned in this clinical trial protocol will be described and justified in a protocol amendment/the statistical analysis plan update and/or in the clinical trial report dependent on the type of deviation.

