5.4.1 Primary Efficacy Endpoint

The primary endpoint will be analysed using a cox proportional hazards model with treatment group, pooled sites, and disease severity at maintenance baseline (as determined by the PGA) as factors. Maintenance baseline is used in the model as compared to baseline at visit 1. See section [5.7](#) for details regarding changes as compared to the protocol.

The survival curves will be estimated using the Kaplan-Meier estimator. A log-log transformation will be applied to the survival function to obtain the pointwise confidence intervals in addition to the confidence intervals for the percentiles of the estimated survival times. The estimated survival curves and the confidence limits will be shown graphically. The percentiles of the estimated survival distribution and 95% confidence limits for the percentiles will be tabulated by treatment group.

Number of subjects still at risk of first relapse at timepoints for scheduled visits will be summarised by treatment group.

Further details for tables, figures and listings for the primary endpoint are given in [Appendix I](#) and [Appendix II](#).

Sensitivity analysis:

In the sensitivity analysis the primary endpoint will be analysed incorporating interval censoring. We will consider three different types of censoring. Subjects who do not encounter a relapse during the trial and subjects who are withdrawn from the trial in the maintenance phase before having a relapse will be right-censored, and the number of days will be treated as a censored observation at the end date of the maintenance phase. Subjects who are confirmed to have a relapse at a scheduled visit are interval censored, and it is assumed that the start of the relapse is between the scheduled visit where the relapse is confirmed and the previous visit where PGA was measured for the subject. For subjects who are confirmed to have a relapse at an unscheduled visit, it is assumed that the relapse starts on the day of this visit. These subjects are assumed to have exact observations. More details are given in [Table 3](#).

The number of subjects without relapse, the number of subjects with relapse confirmed at a scheduled visit, and the number of subjects with relapse confirmed at an unscheduled visit will be summarised by treatment group.

Table 3: Censoring in the sensitivity analysis of primary endpoint

Relapse information	Censoring type	Observation type	Lower endpoint	Upper endpoint

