5.4.2.2 Number of relapses during maintenance phase

The number of relapses will be analysed using a Poisson regression model with treatment group, pooled sites, and disease severity at maintenance baseline as factors, subject as random effect, and time at risk as an offset. REML will be used for estimation. Maintenance baseline is used in the model as compared to baseline at visit 1. See section [5.7](#) for details regarding changes as compared to the protocol.

Number of relapses will be summarised by treatment group. Rates (number of relapses divided by patient years of exposure multiplied by 100) will also be presented.

In addition, the distribution of the relapse rate by treatment group will be presented.

Sensitivity analysis:

The number of relapses will be analysed with a negative binomial regression model with treatment group, pooled sites, and disease severity at maintenance baseline as factors, subject as random effect, and time at risk as an offset. REML will be used for estimation. The purpose of this sensitivity analysis is to account for potential overdispersion in data, which is not adjusted for in the Poisson model.

See section [5.7](#) for details regarding changes as compared to the protocol.

Trial ID: LP0053-1004	Date: 15-JUL-2019	Version: 1.0 Page 17 of 177
-----------------------	-------------------	--------------------------------

More details for the tables and listings can be found in [Appendix I](#) and [Appendix II](#).

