-----------------------	-------------------	--------------------------------

Statistical analysis:

For each of the 100 complete data sets, the total PSI scores will be analysed using a Mixed effect Model Repeat Measurement (MMRM) with treatment group, week (from randomisation), interaction between treatment and week, relapse status, and maintenance baseline total PSI score as fixed factors and subject as random effect. Repeated measurements within subject is modelled using an unstructured variance structure. REML will be used for estimation.

The estimates and standard errors from the 100 analyses will be pooled into estimated least squares means for each treatment group and estimated treatment difference with associated standard errors using Rubin's rule to draw inference. From these pooled treatment estimates, the 95% CI for the treatment difference will be calculated. The p-value for treatment difference will be calculated using a two-tailed Student's t-test based on the pooled estimate. Pooled treatment estimates together with treatment difference, 95% CI and p-value will be presented by week. Furthermore, the pooled treatment estimates will be plotted by week.

Subjects are supposed to complete the PSI questionnaire on a weekly basis the first 28 weeks of the maintenance phase and the 2 last weeks of the maintenance phase (Week 54 to 56) which is only applicable for completers. However, during blind review of data, it is observed that subjects in general forget to complete the questionnaire the last 2 weeks which implies that limited data are available for this period. For this reason, the analysis of the PSI total score will be based on the first 28 weeks of the maintenance phase.

The analysis of PSI will be done for full analysis set.

More details for the tables and listings can be found in [Appendix I](#) and [Appendix II](#).

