Treatment difference	
95% CI	
p-value	

Estimates are obtained from a Mixed effect Model Repeat Measurement (MMRM) including treatment group, days from randomisation, interaction between treatment and time, relapse status, PSI total score at time of randomisation. Multiple imputation is used to impute missing assessment of PSI. Rubin's rule is used to pool the estimates for the inference.

Shell 48: Statistical analysis of DLQI: full analysis set

LEO 90100 vs. vehicle	
Number of subjects randomised to LEO 90100	xxx
Number of subjects randomised to vehicle	xxx
Visit 2	
Estimated means	
LEO 90100	xx.xx
Vehicle	xx.xx
Treatment difference	xx.xx
95% CI	xx.xx-xx.xx
p-value	0.xxx or <0.001
...	
Visit 15	
Estimated means	
LEO 90100	
Vehicle	
Treatment difference	
95% CI	
p-value	

Estimates are obtained from a Mixed effect Model Repeat measurement (MMRM) including treatment group, days from randomisation, interaction between treatment and time, relapse status, DLQI total score at time of randomisation. Multiple imputation is used to impute missing assessment of DLQI. Rubin's rule is used to pool the estimates for the inference.

Shell 49: Shift table for EQ-5D-5L from start to end of open-label phase: open-label safety analysis set

Visit EQ-5D-5L	Open-label safety analysis set (n=xxx)					Randomised subjects (n=xxx)					Not randomised subjects (n=xxx)				
	Visit 2					Visit 2					Visit 2				
	0	1	2	3	4	0	1	2	3	4	0	1	2	3	4
Visit 1															
Mobility															
0: I have no problems walking	xxx	xxx	xxx	xxx	xxx	xxx	xxx	xxx	xxx	xxx	xxx	xxx	xxx	xxx	xxx
1: I have slight problems walking	xxx	xxx	xxx	xxx	xxx	xxx	xxx	xxx	xxx	xxx	xxx	xxx	xxx	xxx	xxx
2: I have moderate problems walking	xxx	xxx	xxx	xxx	xxx	xxx	xxx	xxx	xxx	xxx	xxx	xxx	xxx	xxx	xxx
3: I have severe problems walking	xxx	xxx	xxx	xxx	xxx	xxx	xxx	xxx	xxx	xxx	xxx	xxx	xxx	xxx	xxx
4: I am unable to walk	xxx	xxx	xxx	xxx	xxx	xxx	xxx	xxx	xxx	xxx	xxx	xxx	xxx	xxx	xxx
Self-care															
0: I have no problems washing or dressing myself	xxx	xxx	xxx	xxx	xxx	xxx	xxx	xxx	xxx	xxx	xxx	xxx	xxx	xxx	xxx
1: I have slight washing or dressing myself	xxx	xxx	xxx	xxx	xxx	xxx	xxx	xxx	xxx	xxx	xxx	xxx	xxx	xxx	xxx
2: I have moderate washing or dressing myself	xxx	xxx	xxx	xxx	xxx	xxx	xxx	xxx	xxx	xxx	xxx	xxx	xxx	xxx	xxx
3: I have severe washing or dressing myself	xxx	xxx	xxx	xxx	xxx	xxx	xxx	xxx	xxx	xxx	xxx	xxx	xxx	xxx	xxx
4: I am unable to wash or dress myself	xxx	xxx	xxx	xxx	xxx	xxx	xxx	xxx	xxx	xxx	xxx	xxx	xxx	xxx	xxx

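### The DLQI and PSI mixed models omit pooled site and disease severity, which every regression model for the primary and secondary endpoints includes; adding them is a small, nearly free gain in precision

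*SAP*

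**What the plan says.** SAP 5.4.4.1 analyses total DLQI in each of 100 imputed data sets. The model terms are "treatment group, visit (scheduled), interaction between treatment and visit, relapse status, and maintenance baseline total DLQI score as fixed factors and subject as random effect". It adds: "Repeated measurements within subject is modelled using an unstructured variance structure". SAP 5.4.4.4 does the same for PSI, with "treatment group, week (from randomisation), interaction between treatment and week, relapse status, and maintenance baseline total PSI score as fixed factors", a subject random effect and an unstructured structure. Treatment differences and p-values are reported by visit (DLQI) or week (PSI).

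The table shells agree with the text. The Shell 48 footnote describes the DLQI model as "including treatment group, days from randomisation, interaction between treatment and time, relapse status, DLQI total score at time of randomisation", and Shell 47 is parallel for PSI. The omission of site and severity is therefore the planned model and not a slip in one sentence.

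Protocol 6.3 stratifies randomisation by trial site, HPA axis testing and baseline severity. Protocol 11.3.8 states: "Usually, the statistical analysis of efficacy parameters takes all the stratification factors into account". It then gives reasons for leaving out HPA testing only.

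The primary analysis is a "cox proportional hazards model with treatment group, pooled sites, and disease severity at maintenance baseline" (SAP 5.4.1), and its interval-censored sensitivity model has the same factors. Relapse counts use a "Poisson regression model with treatment group, pooled sites, and disease severity at maintenance baseline as factors" (SAP 5.4.2.2), and the negative binomial sensitivity model matches. For the remission ANOVA, SAP 5.4.2.1 refers back to the protocol, and the Shell 27 footnote names pooled site and severity at maintenance baseline.

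**The concern.** DLQI and PSI are the only patient-reported outcomes with a formal treatment comparison. When the SAP replaced the protocol's t-tests with covariate-adjusted models, it left out two factors that it uses in all its primary and secondary regression models.

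Stratified allocation balances the arms within site, so between-site differences in level largely cancel out of the treatment difference. A model without site leaves those differences in the residual. If site is prognostic, the model-based standard error then exceeds the true variability of the estimate: intervals are wider than the design warrants and tests run below their nominal level. The same reasoning applies to severity as stratified at Visit 1. Severity at maintenance baseline is an ordinary prognostic covariate, so leaving it out only gives up whatever precision it would add.

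The second matter is the covariance wording. A subject random intercept and an unstructured within-subject matrix describe the same covariance twice.

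**Working it through.** The documents state no SD, effect size, power or standard error for DLQI or PSI, so there is no figure of the plan's to reproduce.

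**Inputs**
- SAP Table 8, randomised per pooled site: 132 + 55 + 52 + 68 + 56 + 68 + 114 = 545, in 7 pooled groups formed from 55 sites.
- DLQI: Visits 3 to 15, so 13 post-baseline occasions. PSI: 28 weekly occasions.
- Two-sided 5% level (Protocol 11.3.8).
- R², the share of residual variance that site explains after the baseline score: not in the documents. Assumed range 0% to 10%.

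**1. Upper bound on SE inflation**, with allocation exactly balanced within pooled site. The SE ratio without/with site is 1/√(1 − R²), and the actual level is 2 × [1 − Φ(1.96/√(1 − R²))].

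| R² | SE ratio | Level of a nominal 5% test |
|---|---|---|
| 0% | 1.000 | 5.0% |
| 2% | 1.010 | 4.8% |
| 5% | 1.026 | 4.4% |
| 10% | 1.054 | 3.9% |

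A simulation with the Table 8 sizes (1,500 runs per setting) gave SE ratios of 1.000, 1.011, 1.026 and 1.054. Its rejection rates without site were 4.5%, 3.9%, 4.9% and 3.3%. With a Monte Carlo error of about √(0.05 × 0.95/1500) = 0.6 percentage points, they are too noisy to refine the last column.

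**2. Incompletely filled strata.** Stratification was by individual site, crossed with HPA testing and severity, and SAP 5.6.1 says many centres randomised only a few subjects. If a fraction f of the between-site variance stays in the treatment difference, the inflation is 1/√(1 − (1 − f)R²). A simulation with 55 sites, in which block sizes of 2 to 6, site sizes within pools and the severity/HPA mix were all assumed, put f at about 0.16 to 0.33.
- R² = 5%: 1/√(1 − 0.67 × 0.05) = 1.017 to 1./√(1 − 0.84 × 0.05) = 1.022. The level is then 4.5% to 4.6%.
- R² = 10%: 1/√(1 − 0.067) = 1.035 to 1/√(1 − 0.084) = 1.045.

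**3. Covariance parameters.** An unstructured matrix on p occasions has p(p + 1)/2 parameters.
- DLQI: 13 × 14/2 = 91. A random intercept makes 92; the rank is 91.
- PSI: 28 × 29/2 = 406. A random intercept makes 407; the rank is 406.

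The likelihood depends only on V = R + s²J, where R is the unstructured matrix, J the matrix of ones and s² the subject variance. An unstructured R absorbs any change in s². In a small worked example, s² = 0, 0.1, 0.3, 0.5 and 1.0 all gave −2 log-likelihood 2954.78, treatment estimate −0.525 and SE 0.343. Exactly one parameter is redundant, and nothing that the SAP reports depends on it.

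**The case against.** The protocol's own DLQI and PSI comparisons (11.3.5.1, 11.3.5.4) were t-tests without site, so SAP 5.7, which lists changes from the protocol, had no dropped site term to explain. Protocol 11.3.8 describes usual practice and does not bind every analysis. Both points stand. They explain how the omission arose, but give no reason to keep it once the models carry covariates.

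A reader might infer that these two models are the only tested efficacy analyses without site. They are not: the comparisons of subjects still at risk at weeks 26 and 52 (SAP 5.4.3.1) use a z-test and a binomial test with no site term. The contrast holds for the primary and secondary regression models only.

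A reader might also infer that the standard errors are known to be too large. That depends on site or severity predicting the score after the baseline score, which the documents do not show; at R² = 0 there is no effect. The imputation also draws donor scores without regard to site, which would dilute any site signal.

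Finally, a reader might infer that a random effect beside an unstructured matrix makes the model impossible to estimate. Only the split between the two is unidentified. The marginal covariance, the treatment difference and its SE are identified, and Rubin's rule pools only the estimates and SEs. A software warning is possible, but failure is not established.

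**Conclusion.** The point holds as a modest matter of precision and consistency. Both models omit pooled site and severity without a stated reason, although randomisation was stratified by trial site and baseline severity and all the primary and secondary regression models adjust for pooled site and severity.

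If site explains 2% to 10% of residual variance, the reported SE is too large by at most about 1% to 5%, and by less with incompletely filled strata. That share is an assumption, and the effect may be nil. The direction is conservative. SAP 5.6.4 confines the testing hierarchy to the primary and two secondary endpoints, so the documents do not support reading this as a threat to the trial's main conclusions.

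Two limits apply to the remedy. Pooled site is a grouping of the site factor used at randomisation and recovers only part of it. Severity at maintenance baseline is not the Visit 1 severity used for stratification; adding it brings these models into line with the SAP's others.

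The subject random effect is a wording error with no effect on the reported results.

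**What to change.** - Add pooled sites (Table 8) and disease severity at maintenance baseline as fixed factors to the DLQI and PSI models in SAP 5.4.4.1 and 5.4.4.4.
- Update the footnotes of Shells 47 and 48 to match. They also refer to days from randomisation where the text uses visit or week.
- Delete the subject random effect from both models. Keep subject as the repeated-measures unit for the unstructured covariance.
- Preferably, name a fallback covariance structure in advance, above all for PSI, whose 406 covariance parameters are to be estimated from at most 545 randomised subjects.

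The cost is SAP wording only, with no new data. Pooled sites use 7 − 1 = 6 degrees of freedom. Severity uses one more, because the full analysis set admits only clear or almost clear at randomisation. That is 7 in total against about 545 subjects.
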